6.2. Study Period

6.2.1. Months 3, 9, 15, 21, 27, 33, 39, 45, 51, 57, 63, 69, 75, 81, 87, 93, 99, 105, 111, 117

Subjects will be contacted by telephone, contact is to be made \pm 1 week of scheduled time:

- Ask subjects non-leading questions such as “How do you feel?” and document adverse events.
- Record concomitant medications.
- Mail 3 month supplies of investigational product following telephone contact.
- These phone visits can be conducted in person at the clinic at the discretion of the sites.

6.2.2. Months 6, 12, 18, 24, 30, 36, 42, 48, 54, 60, 66, 72, 78, 84, 90, 96, 102, 108, 114

Subjects will return to the clinic for the following assessments. Visits are to occur \pm 2 weeks of the scheduled time:

- Conduct abbreviated physical examination, including weight and vital signs.

- Collect blood/urine samples for clinical laboratory assessments (section [7.3](#)).
- Perform Patient Global Assessment.
- Determine NYHA Classification.
- Administer Kansas City Cardiomyopathy Questionnaire.
- Conduct 6-minute walk test.
- Ask subjects non-leading questions such as “How do you feel?” and record adverse events.
- Record concomitant medications.
- Determine drug compliance and accountability.
- Dispense 3 month supply of investigational product.

6.2.3. Months 12, 24, 36, 48, 60, 72, 84, 96, 108

In addition to the above assessments, collect ECG and echocardiogram every 12 months.

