The subject should return to the investigational site and be evaluated as soon as possible, preferably within 48 hours from awareness of the abnormal results. This evaluation should include laboratory tests, detailed history and physical assessment. In addition to repeating AST and ALT, laboratory tests should include albumin, creatine kinase, total bilirubin, direct and indirect bilirubin, gamma-glutamyl transferase, prothrombin time (PT)/INR, and alkaline phosphatase. A detailed history, including relevant information, such as review of ethanol, acetaminophen, recreational drug and supplement consumption, family history, occupational exposure, sexual history, travel history, history of contact with a jaundiced subject, surgery, blood transfusion, history of liver or allergic disease, and work exposure, should be collected. Further testing for acute hepatitis A, B, or C infection and liver imaging (eg, biliary tract) may be warranted. All cases confirmed on repeat testing as meeting the laboratory criteria defined above, with no other cause for LFT abnormalities identified at the time should be considered potential Hy's Law cases irrespective of availability of all the results of the investigations performed to determine etiology of the abnormal LFTs. Such potential Hy's Law cases should be reported as SAEs.

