9.1. Sample Size Determination

There is no formal sample size calculation for this protocol. Subjects who completed Protocol Fx1B-201 are eligible; up to 35 subjects are expected to enroll in Protocol Fx1B-303.

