## 7. HANDLING OF MISSING VALUES

Data which are based on entire scales which are missing will be analyzed as follows:

If the data are time until event data and there is no observed event (at any point during the trial) the observation will be censored at the last observation. If there was an observed event, the data associated with the first observation of that event will be used; all other observations will not be needed.

For all other data types, the data will be analyzed as follows: for analyses at each visit, the missing observations will not be used. Any visit after the subject was discontinued will remain as missing data.

For any subject missing a 12-month visit observation from Study Fx1B-201, if the Day 0 visit observation from the Fx1B-303 study is reported, the Day 0 visit observation from the Fx1B-303 will be imputed for the 12-month visit observation for Study Fx1B-201.

For specific scoring details, see [Appendix 1](#).

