**Cardiac Measures:** Changes from baseline (defined as the last evaluation prior to the first dose of study drug) will be summarized for each of the cardiac parameters listed above by visit. Clinically significant changes in ECG measures (as indicated by the items in [Section 6.2, #6](#), item h through m) at any point during the study will be summarized.

Pacemaker and defibrillator insertion procedures will be identified through a programmatic search of potentially related terms in the clinical database coupled with a manual review by Pfizer Clinical.

The following MedDRA Lower Level Terms (codes) will be applied to the Medical History, Adverse Events, and Investigator Comments to identify potential procedures in the clinical

database: CARDIOVERTER PLACEMENT (10053015), INSERTION OF IMPLANTABLE CARDIOVERTER DEVICE (10052044), CARDIAC PACEMAKER INSERTION (10007598), PACEMAKER INSERTION (CARDIAC) (10033352), DEFIBRILLATOR/PACEMAKER INSERTION (10069072), IMPLANTABLE DEFIBRILLATOR INSERTION (10049442).

The following terms will also be searched to identify potential associated procedures collected in the Investigator Comments CRF: pacemaker, implantable cardiac device, ICD, AICD, cardioversion, cardioverter, defibrillator, ventricular fibrillation, ventricular tachycardia.

Final search criteria and categorization of pacemaker and defibrillator will be based on the results of the clinical review and will be described in the programming plan prior to database finalization.

The number and percentage of subjects with pacemaker or defibrillator insertion procedures (defined above) will be summarized by category and for overall at baseline of Fx1B-201, the number and percentage of subjects who have such devices implanted during the course of Fx1B-201 and during the course of B3461026 (Fx1B-303), respectively.

**Vital signs:** Will be summarized using descriptive statistics, to include: values at each visit, change from baseline to each visit and a categorization of clinically significant changes.

Significant changes from baseline are defined as follows:

- Systolic Blood Pressure (mmHg) Decrease (Change  $\leq$  -20, or Value < 90)
- Systolic Blood Pressure (mmHg) Increase (Change  $\geq$  20, or Value > 180)
- Diastolic Blood Pressure (mmHg) Decrease (Change  $\leq$  -15, or Value < 50)
- Diastolic Blood Pressure (mmHg) Increase (Change  $\geq$  15, or Value > 105)
- Heart Rate (bpm) Decrease (Change  $\leq$  -15, or Value < 50)

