### **Appendix 2. Definition and Use of Visit Windows in Reporting**

For the purpose of this study, Day 1 is defined as the first dose day under this protocol.

Day 1  $\pm$  1 week

Every other 3 month telephone visits between clinic visits  $\pm$  1 week

Clinic visits every 6 months  $\pm$  2 weeks

End of study visit  $\pm$  2 weeks

However, in order to maximize the use of all available data, the visit windows for each visit are expanded as follows:

Day 0: End of study visit from Fx1B-201

Day 1 + 1.5 months

Telephone contact (every 3 months between clinic visits)  $\pm$  1.5 months

Clinic visits (every 6 months)  $\pm$  3 months

End of study visit (see details below)

In the event that there is a break between the last visit of the parent study (Fx1B-201,) and the first day of dosing in the current study Fx1B-303 (B3461026); then the visit associated with the first day of enrollment in the current study Fx1B-303 (B3461026) will be the baseline visit of this study.

For an early termination visit within study B3461026 (Fx1B-303): The existing windowing rules will be used and as such, the data in the early termination visit should never replace an existing visit. If the visit covered by the windowing rules above is already populated with an existing visit, then the EOS visit should be mapped forward to the next clinic visit.

As an example, the EOS visit occurs at month 68.

If there is no month 66 visit, then the EOS visit becomes the month 66 visit.

If there is a month 66 visit, then the EOS visit becomes the month 78 visit.

For an unscheduled visit:

If possible, the existing windowing rules will be used, but the data should never replace an existing visit. If the visit is already populated, then the unscheduled visit should be mapped forward to the next appropriate visit for that measure if that visit is available.

As an example, the unscheduled visit occurs at month 68 and the data are collected annually.

If there is no month 66 visit, then the unscheduled visit becomes the month 66 visit.

If there is a month 66 visit, but no month 78 visit then the unscheduled visit becomes the month 78 visit.

If there are both month 66 and month 78 visits, then the unscheduled visit is not included in the summary analyses but is included in the listing as unscheduled.

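### SAP Appendix 2 redates unscheduled values or confines them to listings, without saying whether the QTc any-time counts and vital-sign change categories are exempt

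*SAP*

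**What the plan says.** SAP Appendix 2 widens the reporting windows to ±3 months around each six-monthly clinic visit and gives three outcomes for an unscheduled visit. Its example is a visit at month 68 for data collected annually:

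- Own slot empty: "If there is no month 66 visit, then the unscheduled visit becomes the month 66 visit".
- Own slot filled, next slot empty: "If there is a month 66 visit, but no month 78 visit then the unscheduled visit becomes the month 78 visit".
- Both filled: "then the unscheduled visit is not included in the summary analyses but is included in the listing as unscheduled".

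Four other provisions bear on this:

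- SAP 8.3 says that clinically significant ECG changes (Section 6.2, item 6, h to m, which are the QTc thresholds and QTc changes) "at any point during the study will be summarized". Vital signs are summarised by visit with a categorisation of significant changes, and no comparable whole-study wording. Laboratory tests get by-visit descriptive statistics.
- SAP Section 7: "Any visit after the subject was discontinued will remain as missing data".
- Protocol 6.2.3, headed months 12, 24 and so on to 108: "In addition to the above assessments, collect ECG and echocardiogram every 12 months".
- Protocol 8.5.1, on suspected liver injury: "The subject should return to the investigational site and be evaluated as soon as possible, preferably within 48 hours from awareness of the abnormal results". Such repeat tests will usually fall outside the six-monthly schedule.

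**The concern.** Unscheduled measurements are often taken because something has gone wrong. Appendix 2 ranks values by whether the visit was scheduled and takes no account of which value is worse. For a subject with complete visits, every unscheduled value goes to the listings alone. Where the next slot is empty, the value is shown under a visit at which it was not measured.

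Long-term safety is a stated objective. What is at stake is whether the vital-sign change categories and the whole-study QTc counts include these measurements, and whether the by-visit columns show values at the right time.

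**Working it through.** **1. Reproduce the SAP example.** The month 66 window is 66 − 3 = 63 to 66 + 3 = 69, so month 68 lies inside it. Applying the rule gives month 66, month 78 or listing only, as the SAP states.

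**2. Size of the date shift.**

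- Month 68 shown as month 78: 78 − 68 = 10 months late.
- The month 78 window opens at 78 − 3 = 75, so the value precedes it by 75 − 68 = 7 months.
- For a six-monthly measure the next slot is month 72, a shift of 72 − 68 = 4 months. In general, a value within ±3 months of visit *s* that moves to *s* + 6 arrives 3 to 9 months late.
- If annual measures are assigned to the nearest annual slot (an assumption, since Appendix 2 gives no separate annual window), the shift is 6 to 18 months.

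**3. Compare the example with the protocol schedule.** 66/12 = 5.5 and 78/12 = 6.5, so neither month is an annual visit; the nearest are months 60 and 72. Counting from the start of the 12-month parent study does not help: 66 + 12 = 78 and 78 + 12 = 90, and 90/12 = 7.5. The end-of-study example in Appendix 2 has a related fault. Its text sends the data to the next clinic visit, which after month 66 is month 72 (Protocol 6.2.2), but the example says 78.

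**4. Compare with SAP Section 7.** Take an invented subject seen at month 66 and, unscheduled, at month 68, who dies at month 70. SAP 6.5 counts death among discontinuations. Months 72 and 78 are empty. Followed literally, Appendix 2 places the month 68 value at month 72 (six-monthly measure) or month 78 (the SAP's annual example), whereas Section 7 keeps both missing.

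**5. How often each branch applies.** Let *p* be the chance that a scheduled slot is empty, independently between slots. The documents give no value, so 0% to 30% is assumed. Kept in own slot = *p*; moved forward = (1 − *p*)*p*; listing only = (1 − *p*)².

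| *p* | Own slot | Moved forward | Listing only |
|---|---|---|---|
| 0% | 0% | 0% | 100% |
| 10% | 10% | 9% | 81% |
| 20% | 20% | 16% | 64% |
| 30% | 30% | 21% | 49% |

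These are shares of unscheduled values. The documents do not say how many such values to expect, so no count of affected subjects can be derived.

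**6. Consequence by measure.**

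- *Vital signs:* no whole-study wording offsets Appendix 2. An unscheduled systolic pressure below 90 mmHg, one of the listed criteria, can go uncounted when both slots are filled.
- *QTc:* SAP 8.3 counts crossings over the whole study; Appendix 2 bars some values from the summary analyses and makes no exception. The SAP does not say which governs.
- *Laboratory tests:* unscheduled values can be missing from, or misdated in, the by-visit statistics. No worst-value or threshold table is planned.

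**The case against.** A reader might infer that QTc outliers are left out of the safety tables. The documents do not establish that. Appendix 2 concerns visit windows, and the natural reading is that it governs by-visit tables while SAP 8.3 governs the whole-study QTc count. What stands is the missing statement of precedence. A calculation of how rarely an annual ECG would catch a brief QTc excursion would describe the protocol's schedule and would not measure this defect.

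A reader might also infer that liver-test outliers are suppressed. There is no liver outlier table to be left out of. Abnormal tests that need further testing or intervention are reported as adverse events (Protocol 8.4), confirmed potential Hy's Law cases as serious adverse events (8.5.1), all laboratory measures are listed (SAP 6.2), and a safety board reviews cumulative data (SAP 3.1). These routes yield event terms and listings and do not supply numerical outlier counts, but they substantially reduce the clinical risk.

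Nor is it true that only scheduled checks are counted, because a value whose own slot is empty stays in the summaries. Forward mapping also applies only if the later visit is available, an undefined condition that might exclude visits after discontinuation; and a withdrawn subject's end-of-study data may already occupy the slot. The conflict with Section 7 is therefore a possible result of literal programming, not a certain one.

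Finally, keeping event-triggered values out of by-visit means is defensible because it limits selection bias. That stands, and the fix preserves it. It does not justify moving a value to a later visit or omitting it from a count of significant changes.

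**Conclusion.** The point holds in a limited form. The forward mapping is wrong by the SAP's own windows and by the protocol's annual schedule: 10 months late in the SAP's example, and 3 to 9 months on the six-monthly grid. It can also conflict with Section 7. The vital-sign change categories have no protection from the listing-only rule. The QTc any-time count has apparent protection, but the two provisions are not reconciled.

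The loss is partial. The branch shares rest on assumed, independent rates of empty slots, and the number of unscheduled values is unknown. In a descriptive single-arm study of up to 35 subjects with individual listings, this affects how safety is tabulated and threatens no hypothesis test. It should still be corrected, because long-term safety is an objective and the remedy is cheap.

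**What to change.** 1. State in SAP 8.3 and Appendix 2 that the QTc any-time counts (items h to m) and the vital-sign significant-change categories use every post-baseline value, scheduled or not, and are exempt from the Appendix 2 visit rules.
2. Let an unscheduled value enter a by-visit table only within that visit's own window and only when the scheduled value is missing. Never map it to a later visit.
3. Correct the month 66/78 example to the protocol schedule. With ±3-month windows, month 68 lies between the annual windows of 57 to 63 (month 60) and 69 to 75 (month 72), so an annual measure would enter no by-visit column. A six-monthly measure could fill month 66 if that value is missing.

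A table of worst post-baseline ALT, AST and total bilirubin against the Protocol 8.5.1 thresholds would be a useful option, but it is a new analysis and not a repair of Appendix 2.

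The cost is SAP wording and analysis-dataset flags, with no new data. Outlier percentages may look slightly less favourable. Fewer unscheduled values will enter by-visit tables: on the six-monthly grid the excluded share becomes 1 − *p*, or 90%, 80% and 70% at the assumed rates of 10%, 20% and 30%, against 81%, 64% and 49% now. The any-time QTc counts and vital-sign categories will still include them.

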### **Appendix 3. Algorithm for imputing missing last dosing date of study drug**

If the last dosing date is missing and the subject has discontinued from the study, the following method will be used to impute the missing last dosing date.

If the subject discontinues prior to the next expected visit date (last visit plus 90 days) regardless of reason for discontinuation then the last dosing date is the date of discontinuation or death whichever is first .

If the subject discontinues after the next expected visit date (last visit plus 90 days) then the following will be examined. Note that the use of July 1, 2013 in the algorithm reflects the change in capsules dispensed.

If the last visit was a telephone contact and the last visit is prior to or equal to July 1, 2013 then last dosing day = (last visit + 5 months [151 days]) or date of death or date of discontinuation whichever is first.

If the last visit was a telephone contact and the last visit is after to July 1, 2013 then last dosing day = (last visit + 4.5 months [136 days]) or date of death or date of discontinuation whichever is first.

If the last visit was a clinic visit and the last dosing date is prior to or equal to July 1, 2013 then last dosing day = (last visit + 4 months [121 days]) or date of death or date of discontinuation whichever is first.

If the last visit was a clinic visit and the last dosing date is after to July 1, 2013 then last dosing day = (last visit + 3.5 months [106 days]) or date of death or date of discontinuation whichever is first.

If there is a partial date of last dose which is just the year of last dose then use the previous rule. If the partial date is a month and year then the last dosing date = maximum of last date of the partial date month or the result of the rule whichever is first.

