5.2.2. Preparation and Dispensing

Investigational product will be dispensed to subjects according to the following schedule:

- On Day 0, an initial 3-month supply of investigational product will be dispensed to subjects at the clinical unit. Subjects will take their first dose of investigational product at home beginning on Day 1 (i.e., first dose).
- At 3-month intervals between clinic visits, 3-month supplies of investigational product may be mailed from the clinical site directly to subject's home.
- Every six months subjects will return to the clinical unit and will be instructed to bring all investigational product and packaging with them to determine investigational product compliance and accountability. At these clinic visits, 3-month supplies of investigational product will be dispensed directly to subjects for self-administration at home.

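### SAP Appendix 3 does not hold the imputed last dosing date within the recorded year when only the year of last dose is known

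*SAP*

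**What the plan says.** SAP Appendix 3 covers subjects who discontinued without a recorded last dosing date. If they left before the "next expected visit date (last visit plus 90 days"), the discontinuation or death date is used, whichever is earlier. If they left later, a fixed offset is added to the last visit, and the result is cut back to death or discontinuation where either comes first.

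The four offsets are:

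- Telephone contact, up to the cut-off: "prior to or equal to July 1, 2013 then last dosing day = (last visit + 5 months [151 days"
- Telephone contact, after it: "after to July 1, 2013 then last dosing day = (last visit + 4.5 months [136 days"
- Clinic visit, up to the cut-off: "prior to or equal to July 1, 2013 then last dosing day = (last visit + 4 months [121 days"
- Clinic visit, after it: "after to July 1, 2013 then last dosing day = (last visit + 3.5 months [106 days"

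The only explanation is: "Note that the use of July 1, 2013 in the algorithm reflects the change in capsules dispensed". The appendix gives no capsule count and no carry-over rule.

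For partial dates, the year-only instruction is: "If there is a partial date of last dose which is just the year of last dose then use the previous rule". Where month and year are known, the next sentence does bring in the end of the recorded month.

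Protocol section 5.2.2 describes the clinic supply this way: "At these clinic visits, 3-month supplies of investigational product will be dispensed directly to subjects for self-administration at home". It also calls the mailed supply a 3-month supply. Section 5.2.1 says capsules come in 10-count blisterpacks.

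**The concern.** A recorded year is real information: the last dose fell between 1 January and 31 December of that year. Sending the record to the general rule discards it. The algorithm is deterministic, so a program written to the SAP would return a date that the case report form rules out and carry it into treatment duration.

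The telephone offset raises a separate question. The appendix links the cut-off to the amount dispensed, so the offsets look like days of capsules in hand. A smaller dispensing would then be expected to shrink both the newly mailed supply and what is left from the last clinic visit. The telephone offset falls by 15 days (151 to 136), the same as the clinic offset (121 to 106), as if only one of the two had shrunk.

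**Working it through.** **A. Year-only dates**

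Inputs: the offset of 106 days for a clinic visit after 1 July 2013, the 90-day test and the cap, all from Appendix 3. The subject is a constructed example: last visit in clinic on 1 December 2014, last dose recorded as 2014, discontinued in June 2015.

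1. Next expected visit: 1 December 2014 + 90 days = 1 March 2015. Discontinuation is later, so the offset applies.
2. Imputed date: 1 December 2014 + 106 days. Thirty days reach 31 December 2014, leaving 106 − 30 = 76. January and February 2015 take 31 + 28 = 59, leaving 17. Result: 17 March 2015.
3. Cap: June 2015 is later than 17 March 2015, so it does not act.
4. Latest date compatible with the record: 31 December 2014. The imputed date is 76 days beyond it.

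The rule can also fall short. With a last clinic visit on 1 June 2014, last dose recorded as 2015 and discontinuation in 2015, 1 June 2014 + 106 days = 15 September 2014. That is 108 days before 1 January 2015, the earliest date the record allows.

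Neither result depends on what the offsets mean.

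**B. Telephone offset**

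The 121- and 106-day clinic offsets are read here as one dispensing. This is an inference, since Appendix 3 does not say so. On the scale of the bracketed day counts, three months is 91 days. The carry-over model is:

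telephone offset = clinic supply − 91 + mailed supply

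| Situation | Calculation | Result | SAP |
|---|---|---|---|
| Before the change | 121 − 91 + 121 | 151 | 151 |
| After, both supplies reduced equally | 106 − 91 + 106 | 121 | 136 |
| After, last clinic supply still old | 121 − 91 + 106 | 136 | 136 |
| After, only the clinic supply reduced | 106 − 91 + 121 | 136 | 136 |
| Fixed addition to the clinic offset | 121 + 30; 106 + 30 | 151; 136 | 151; 136 |

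The third row is transitional. It runs to about 30 September 2013 (1 July + 91 days), or about 21 October 2013 at the extremes of the visit windows (91 + 14 + 7 = 112 days). The fourth and fifth rows would hold permanently.

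Under the second row the excess is 136 − 121 = 15 days, or 14 to 16 for an interval of 90 to 92 days. The cap limits it further:

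| Death or discontinuation, days after the contact | Excess |
|---|---|
| up to 121 | 0 |
| 125 | 4 |
| 130 | 9 |
| 136 or more | 15 |

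Neither 121 nor 106 is a whole number of 10-count packs. With equal supplies of 100 or 110 capsules after the change, the same model gives 109 or 129 days, and the excess would be 27 or 7 days.

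**The case against.** On year-only dates, the best defence is practical. Such records may be rare, a programmer might add the bound unprompted, and SAP section 8.3 refers the treatment-duration listing to sponsor reporting standards, which may contain a partial-date convention. None of this repairs Appendix 3, which gives an explicit instruction without a bound.

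On the telephone offset the opposing case is strong and mostly stands. A reader might infer that 136 days is about 15 days too long. The documents do not support that as fact. Appendix 3 states no supply figures, and the 121-day result needs equal clinic and mailed quantities after the change. The protocol's shared label of a 3-month supply cannot establish equality, because on this reading the same label covered both 121 and 106 days. A mailed supply left unchanged, or a fixed 30-day addition, reproduces every offset, although no document states either one.

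Two further inferences also fail. The offset of 136 days exceeds 91 days by 45, but this does not contradict Protocol section 5.2.2: a 3-month supply is nominal there, no count is given, and some overage is plausible with visit windows of one to two weeks. Nor is exposure always overstated. Missed doses make capsules last longer, product brought to clinic for accountability is not said to be taken back, and the year-only rule can err in either direction.

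**Conclusion.** The year-only rule is deficient as written. It can return a date that the recorded year excludes, by 76 days in the example, and this rests on no assumption about supply.

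The 136-day offset is unexplained rather than shown to be wrong. If clinic and mailed supplies were equal after 1 July 2013, with the clinic offsets taken as one dispensing, it is up to 15 days too long once both supplies are of the new size. It is then not too long at all for a subject who died or discontinued within 121 days of the contact.

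The consequences are small. The use visible in the documents is the treatment-duration listing in SAP section 8.3. Mortality censoring there uses the last visit, discontinuation or transplant, and SAP section 6.4 defines treatment-emergent events by the course of the study. Protocol section 9.1 expects at most 35 subjects. The number with a missing or year-only last dosing date is not given, but is probably small. Severity is low.

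**What to change.** 1. In the year-only sentence of Appendix 3, limit the imputed date to 1 January–31 December of the recorded year, still capped at death or discontinuation. If death or discontinuation precedes that year, query the record instead of imputing.
2. State the clinic and mailed quantities before and after 1 July 2013 and the carry-over rule, and check the 136 days against them. If the quantities were equal after the change, keep 136 only where the preceding clinic supply was of the old size, and derive the later offset from the actual quantities (121 days if each was a 106-day supply). If only the clinic supply was reduced, keep 136 and say why.
3. In the same edit, make the clinic branches test the last visit date, as the telephone branches do. They now test the last dosing date, which is the quantity being imputed.

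The cost is a few lines of SAP text and a small programming change. No new data are needed beyond the dispensing records.

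### SAP Appendix 3: the clinic-visit rules for a missing last dosing date test that same date, and the month-and-year rule asks for both the later and the earlier date

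*SAP*

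**What the plan says.** The algorithm in SAP Appendix 3 starts from this condition: "If the last dosing date is missing and the subject has discontinued from the study". A subject who discontinues within 90 days of the last visit gets the earlier of discontinuation and death. Otherwise supply-based rules apply: "If the subject discontinues after the next expected visit date (last visit plus 90 days) then the following will be examined". These add a fixed number of days to the last visit and cap the result at death or discontinuation.

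The number of days depends on contact type and on a cut-off, explained as follows: "Note that the use of July 1, 2013 in the algorithm reflects the change in capsules dispensed".

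- Telephone, 151 days: "If the last visit was a telephone contact and the last visit is prior to or equal to July 1, 2013"
- Telephone, 136 days: "If the last visit was a telephone contact and the last visit is after to July 1, 2013"
- Clinic, 121 days: "If the last visit was a clinic visit and the last dosing date is prior to or equal to July 1, 2013"
- Clinic, 106 days: "If the last visit was a clinic visit and the last dosing date is after to July 1, 2013"

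A partial date with only the year is sent back to these rules. When month and year are known, the last dosing date is the "maximum of last date of the partial date month or the result of the rule whichever is first".

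**The concern.** The two telephone rules compare the last visit, a known date, with 1 July 2013. The two clinic-visit rules compare the last dosing date with it, which is the unknown that the algorithm is meant to supply. A programmer must either guess a branch and check whether the answer agrees with the guess, or silently substitute another date.

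The month-and-year rule joins two opposite instructions. A maximum of two dates is the later one; whichever is first is the earlier one. Nothing else in the SAP or protocol says which governs.

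An imputation rule is written in advance so that independent programmers derive the same date. Here they need not. The date feeds treatment duration, which SAP Section 8.3 lists for each subject, in a study whose first objective is long-term safety and efficacy data.

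**Working it through.** **Offsets.** Appendix 3 gives 5, 4.5, 4 and 3.5 months as 151, 136, 121 and 106 days. The formula 30 × months + 1 reproduces all four. The two clinic offsets differ by 121 − 106 = 15 days.

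**Clinic-visit rules.** Let V be the last clinic visit, and assume first that no death or discontinuation cap applies.

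- The 121-day branch agrees with its own condition if V + 121 ≤ 1 July 2013, that is, V ≤ 2 March 2013.
- The 106-day branch agrees with its own condition if V + 106 > 1 July 2013, that is, V ≥ 18 March 2013.

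| V | Branch meeting its own condition | Branch if the last visit is tested | Consequence |
|---|---|---|---|
| To 2 March 2013 | 121 | 121 | None |
| 3 to 17 March 2013 (15 dates) | Neither | 121 | No solution as written |
| 18 March to 1 July 2013 (106 dates) | 106 | 121 | 15 days apart |
| From 2 July 2013 | 106 | 106 | None |

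Example: V = 15 May 2013 gives 29 August (106 days) or 13 September 2013 (121 days).

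Now add the cap, with death or discontinuation at V + d. The gap between the branches is min(121, d) − min(106, d):

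- d = 106 or less: 0 days
- d = 110: 110 − 106 = 4 days
- d = 115: 115 − 106 = 9 days
- d = 121 or more: 15 days

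If the subject discontinues by 1 July 2013, the last dose cannot be later than that, so the 121-day branch applies under either test. The wording therefore matters only when discontinuation falls after both 1 July 2013 and V + 106. A recorded year other than 2013, or a recorded month other than July 2013, also settles the branch.

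**Month-and-year rule.** Three cases, each with the last contact a clinic visit after 1 July 2013, so the offset is 106 days:

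1. V = 15 February 2014, recorded month March 2014, no death or discontinuation before 1 June. Rule result: 15 February + 106 = 1 June 2014. Later-of gives 1 June; earlier-of gives 31 March. Gap: 30 + 31 + 1 = 62 days, and the later date contradicts the recorded month.
2. The same subject discontinuing on 20 May (V + 94). Rule result: 20 May. Gap to 31 March: 30 + 20 = 50 days.
3. V = 25 January 2014, death on 5 May 2014 (V + 100), recorded month May. V + 106 would be 11 May, so the cap gives 5 May. Later-of gives 31 May, which is 31 − 5 = 26 days after death.

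When the rule result falls inside the recorded month, the two readings differ by 0 to 30 days.

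**Where the date is used.** SAP Section 8.3 lists treatment duration by subject. SAP Section 6.4 defines treatment-emergent events by their occurrence during the study, not by last dose. SAP Section 8.3 censors mortality at last visit, discontinuation or transplant. The SAP specifies no exposure-adjusted rate.

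**The case against.** The strongest reply is that these are drafting slips whose intent can be recovered. The telephone rules test the last visit. The cut-off reflects a change in dispensing, and Protocol Section 5.2.2 ties clinic dispensing to the visit. Every supply-based rule ends by taking the first of its dates, as the month-and-year sentence does. For most clinic-visit dates the branch can be inferred. The circularity touches about four months of visits in a study of up to 10 years and up to 35 subjects.

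Most of this stands, and it sets the size of the point. It does not remove it. For 3 to 17 March 2013 no branch satisfies its own condition. For 18 March to 1 July the answer that satisfies the text literally differs from the likely intended one. The conflict in the month-and-year rule has no calendar limit.

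Three stronger readings are tempting, and the documents do not support them:

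- A reader might infer that the clinic-visit rules cannot be applied at all. They give one answer outside the window above.
- A reader might take 15 days as the error for each affected subject, or 62 days as typical. The first is a maximum that the cap can shrink to nothing. The second assumes no death or discontinuation before 1 June 2014.
- A reader might infer that safety rates or survival results are distorted. No exposure-based rate is specified, and neither treatment-emergence nor mortality censoring uses this date.

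**Conclusion.** Both defects are in the current text, and nothing elsewhere resolves them. The circular condition leaves no solution for last clinic visits from 3 to 17 March 2013. For visits from 18 March to 1 July 2013 it gives a difference of up to 15 days. In both periods it matters only with discontinuation after 1 July 2013 and after V + 106, and with no partial date that settles the branch. The month-and-year wording is the larger problem: read as a maximum, it can override a recorded month or place the last dose after death.

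The visible impact is confined to the treatment-duration listing. How many subjects have a missing or partial last dosing date is not given, so the effect on total exposure cannot be computed. This is a minor correction worth making because some results are wrong or undefined as written and the edit is cheap.

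**What to change.** Edit three sentences in SAP Appendix 3:

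1. In each of the two clinic-visit rules, compare the last visit, not the last dosing date, with 1 July 2013. Every clinic-visit date then has one result: V + 121 up to and including 1 July 2013 and V + 106 afterwards, subject to the existing cap.
2. In the month-and-year rule, delete the reference to a maximum, so that the rule takes the earlier of the last day of the recorded month and the rule result. That result is already capped at death and discontinuation, so they need not be listed again.

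The earlier-of rule can still return a date before the recorded month. For example, a clinic visit on 15 January 2014 gives 1 May 2014 even if June is recorded and discontinuation is later. The sponsor may therefore want a floor at the first day of the recorded month. If one is added, state that it does not override the cap at death or discontinuation.

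The cost is a short SAP edit and the matching change in derivation code. No new data are needed.
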